## 1. Protocol Synopsis

### Observational Synopsis

Protocol Number:	UCDC 5117
Protocol Title:	Comparative Effectiveness of Treatment in Rare Diseases: Liver Transplantation vs. Conservative Management of Urea Cycle Disorders
Study Chair:	[name] [name]
Statistician:	[name]
Consortium:	Urea Cycle Disorders Consortium
Participating Sites:	Children's National Health System The George Washington University National Urea Cycle Disorders Foundation
Activation Date:	March 4, 2016
Sample Size:	Aim 1: 185 (92 with liver transplant, 93 without liver transplant) Aim 2: 32-48 primary caretakers, 25-40 providers Aim 3: 64-48 primary caretakers
Target Enrollment Period:	3 years
Study Design:	Mixed method concurrent study design. Quantitative research methods to address primary outcomes. Qualitative research methods to obtain information on the UCD patient/family experience when making critical treatment decisions
Primary Study Objective:	To study two urea cycle disorder (UCD) patient cohorts, one managed conservatively and the other treated by liver transplantation; comparing survival rate, neurocognitive function and patient-reported quality of life. ( Aim 1 )
Secondary Study Objective:	To examine, through a representative sample of pediatric patient's primary caretakers (typically a parent) and medical providers, including the treating physician and other clinicians on the team, how UCD treatment decisions are made, describing the factors that influence the patient/family's decision to continue conservative management or elect liver transplantation. ( Aim 2 ) To develop a dissemination strategy for study findings of Aim 1 that aligns with the decision-making considerations and process illustrated through Aim 2 and which is responsive to the expressed needs of UCD patients and their primary caretakers. ( Aim 3 )
Study Population and Main Eligibility/Exclusion Criteria:	Aim 1 
 
- Age 18 and under
 
- Diagnosed with the following neonatal-type
 

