### **3.3.2. Liver Transplantation and Outcome**

Liver transplantation for UCD patients was initiated in the early 1990's, before alternate pathway medical therapy was widely available. There were anecdotal case reports of liver transplantation in four of the urea cycle disorders (CPSD, OTCD, ASD, and ALD) [13, 15, 22]. A larger survey of 16 US patients who had received liver transplants from four major transplant centers found that 14 of these cases had survived at least 1-6 years [14]. Their neurological status post-transplantation was in most cases moderately to severely impaired and correlated closely with their condition prior to transplantation. However, the quality of their lives seemed to have improved. Subsequently, to determine if aggressive medical therapy could improve the outcome of severe infantile onset UCD, 5 such cases were monitored at Baylor College of Medicine before and after liver transplantation, including 2 males with OTCD, 2 with CPSD, and one female with OTCD deficiency and intractable hyperammonemia [23]. Three of these infants had serial developmental testing (Griffiths scale) before and after transplantation. It was found that their pre-transplantation overall developmental scales (51, 86, 56) were stabilized after transplantation (70-83, 80-76, 51-47, respectively). Therefore, the authors recommended that early transplantation be considered as the treatment of choice in these severely affected infants.

Most recently, a retrospective analysis of 186 patients with UCD who underwent liver transplantation, [24] showed an increased frequency of liver transplantation for UCD and organic acidemia over the last decade, with 5-year survival rates of 88-99% depending on age. In summary, liver transplantation is now performed frequently to treat UCD and survival seems to have improved over time. However, the outcome of neurocognitive function following liver transplantation is unclear, and it is unknown how it compares to conventional conservative management.

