### **3.3.4. Gaps in Knowledge to be Addressed by this Project**

In spite of a number of reports (mostly case reports) on UCD, the mortality rate from these disorders remains uncertain. A mortality rate of up to 50% has been quoted in the literature for patients with neonatal onset UCD [22]. However, we have seen much lower mortality rates among the UCDC longitudinal study cohort (23%-34%) but it is unclear whether this discrepancy reflects a real improvement in the management of UCD during the last two decades or whether there exists an ascertainment bias; an effort is underway in the UCDC to remove survivorship bias and reassess the risk of mortality. Conservative management and liver transplantation are associated with mortality and morbidity, due to hyperammonemia in the former, and peri- and post-surgical complications in the latter. It is, therefore, important that we have information to compare survival as well as other outcomes of the two approaches, taking appropriate account of specific disorders ( a type of UCD) and severity (neonatal or late onset). The second major gap in knowledge is with respect to neurocognitive outcome in patients with UCD. While we have both cross-sectional and longitudinal information about patients with UCD managed conservatively [8, 26], we need more information about patients with UCD who underwent liver transplantation. Our collaboration with SPLIT (Studies of Pediatric Liver Transplantation) will enable us to capture all or most patients with UCD who undergo liver transplantation and thus provide a nonbiased evaluation of their outcomes. The third gap in knowledge is regarding the quality of life in patients with UCD, both those managed conservatively and by liver transplantation. Although being on a restrictive diet contributes to a compliance issue, and has been shown to have a detrimental effect on children's quality of life [27], no comparisons with other treatments have been reported. Last but not least, there is a paucity of evidence

about how patients with UCD, their families, and their providers reach a shared decision on which management strategy to choose, how frequently and by what mechanisms these decisions are revisited, and what clinical, social, and/or system level factors influence this decision process. To date, there have been no published studies that examine the experience of providers or patients with UCD and their families in making this critical and difficult treatment decision.

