## 6.2. Analysis Plan

For **Aim 1**, we will use covariate balancing propensity scoring based on the CBPS package in R [28] to create comparable (balanced) groups based on their risk factor (covariate) profile in subjects according to their propensity (probability) to move from conservative management to liver transplantation. This approach leads to a model that predicts treatment assignment (conservative vs. liver transplantation) and balances covariates, especially those related to study outcome(s), and offers the best opportunity to simulate RCT results from observational data. From prior experience, many through the UCDC [26,31,32], we know many of the important risk factors, which include neonatal vs. late onset, number of prior hyperammonemic events, event severity in terms of hyperammonemic coma score [2], ammonia and glutamine levels at regularly scheduled clinic visits, and duration from birth to transplant or index date. In addition to these, we will consider comorbidities, organ function, and other laboratory assessments. The CBPS software will help us choose the model that maximizes covariate balance and generate the CBPS for each participant. The next steps will be to order the dataset according to the CBPS. It is useful at this point to select CBPS to cut points to form homogeneous strata to assess the number of subjects with a liver transplant and conservative management per stratum. Those strata where there are

insufficient numbers (mismatches) of conservative treatment or liver transplant subjects will be described, documented and excluded from the primary analysis due to lack of covariate balance. Before conducting model-based analyses for **Aim 1**, we will compare survival times based on the log-rank test in Kaplan-Meier analysis and the difference between mean scores based on t-tests by treatment for neurodevelopment and quality of life within each stratum to evaluate evidence of heterogeneity. Evidence of heterogeneity will provide clues to interactive effects based on UCD severity which will be modeled in regression analyses below by including a cross products term of treatment type with CBPS. Based on these results, we will develop general linear random effects longitudinal regression models in STATA 14

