[<http://www.stata.com/stata14/>] to perform analysis of covariance that will enable us to evaluate **Aim 1** outcomes of neurodevelopment and quality of life. Each model will include treatment type, the baseline measurement of each outcome, as well as the CBPS and if necessary the cross product of treatment type by CBPS. When we address survival, we will implement Cox Regression models to predict survival time by treatment and will either control for CBPS or stratify on it in the case of heterogeneity.

We used PASS 12 [33] to evaluate statistical power to address study aims for sample sizes per group (liver transplantation vs. conservative management) of 90 and 80 in 2-tailed testing at an alpha of 0.05, which assumes some losses in the sample entering analysis in order to maintain adequate covariate balance between groups. For neurodevelopmental and quality of life assessments, we have 80% power to detect modest 0.4sd effect size differences between groups assuming two repeated measurements per person correlated at 70% (ICC). For mortality, assuming the rate in the conservatively treated group remains about 28%, the study will have 80% power to detect and increase in the liver transplant group of about 60% which is robust to differences in sample size between 80 and 90 per group. The study is well powered to detect any clinically meaningful difference in neurocognitive outcomes and QOL and adequately powered to detect a moderate difference in mortality between groups.

For **Aim 2**, interview data will be managed using QSR International NVivo 10 software [[http://www.qsrinternational.com/products\\_nvivo.asp](http://www.qsrinternational.com/products_nvivo.asp)], a program that allows us to collect, organize, and code qualitative data sources. Although not explicitly a grounded theory study, our approach to the analysis of primary caretaker and provider interview data will borrow from aspects of Strauss and Corbin's systematic procedures for grounded theory work [34]. No existing framework or theory currently exists that describes the process which UCD patients and their families undertake when making the difficult decision to pursue liver transplant or continue conservative management. Thus, some of Strauss and Corbin's analysis techniques are suitable for this study aim, which seeks to describe a process/experience in a field where there is little pre-existing evidence.

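### The stated 80% power for mortality does not reproduce: a 60% relative increase over 28% gives about 60–67%, and the direction may be reversed

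*Combined protocol and SAP*

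**What the plan says.** The primary objective in the Protocol Synopsis covers two cohorts, "comparing survival rate, neurocognitive function and patient-reported quality of life". Survival is therefore one of three primary outcomes.

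The power paragraph in section 6.2 uses "sample sizes per group (liver transplantation vs. conservative management) of 90 and 80 in 2-tailed testing at an alpha of 0.05". Losses needed to keep covariate balance are already allowed for in those numbers. For mortality, "assuming the rate in the conservatively treated group remains about 28" per cent, "the study will have 80% power to detect and increase in the liver transplant group of about 60" per cent. The plan calls this robust between 80 and 90 per group and concludes that the study is "adequately powered to detect a moderate difference in mortality between groups".

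The survival analysis in section 6.2 has two parts. Within propensity strata, "we will compare survival times based on the log-rank test in Kaplan-Meier analysis"; the main comparison is a Cox model that adjusts for the propensity score or stratifies on it.

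Two background figures bear on the sentence. Section 3.3.4 reports 23%–34% mortality in the consortium's longitudinal cohort. Section 3.3.2 describes a retrospective series of 186 transplanted patients "with 5-year survival rates of 88-99% depending on age".

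**The concern.** The sentence is garbled at the point where it defines the effect. It does not say whether 60% is relative or absolute, over what period the 28% applies, or which test was used. Its word is an increase, yet a 60% relative increase over 28% is too small to give 80% power with 80 to 90 per group.

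This figure is the only support for the claim that mortality is adequately powered. Mortality risk is the first question in the protocol's Overview (section 1.1), and Aim 3 plans to disseminate the Aim 1 findings to families. If the power is overstated, a non-significant survival comparison could be passed on as evidence that transplantation adds no risk.

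**Working it through.** **Inputs.** Two-sided alpha 0.05, n = 80 or 90 per group, conservative-group mortality p1 = 0.28, change of about 60%, stated power 80% (all section 6.2). I take 28% as cumulative mortality because it lies near the middle of the 23%–34% in section 3.3.4: (23 + 34)/2 = 28.5.

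**Formulas.**
- Two proportions (pooled z-test): power = Φ{[|p2 − p1| − 1.96·√(2·p̄(1 − p̄)/n)] / √([p1(1 − p1) + p2(1 − p2)]/n)}, where p̄ is the mean of p1 and p2.
- Log-rank (Schoenfeld): HR = ln(1 − p2)/ln(1 − p1); deaths d = n(p1 + p2); power = Φ(|ln HR|·√d/2 − 1.96).

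**The plan's figure, read as a relative increase.** p2 = 1.6 × 0.28 = 0.448.
- Two proportions, n = 80: (0.168 − 1.96 × 0.0761)/0.0749 = 0.252, so power is 60.0%. With n = 90: 65.1%.
- Log-rank: HR = ln(0.552)/ln(0.72) = 1.81. With n = 80, d = 80 × 0.728 = 58.2 and power is 61.9%. With n = 90, d = 65.5 and power is 67.0%.
- A simulated log-rank test (exponential survival, equal follow-up, 20,000 trials) gave 60.8% and 65.7%.

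The stated 80% is not reproduced.

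**Other readings** (power at n = 80 / n = 90):

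| Reading | Transplant mortality | Two proportions | Log-rank |
|---|---|---|---|
| 60% relative increase | 44.8% | 60.0 / 65.1% | 61.9 / 67.0% |
| Hazard ratio 1.6 | 40.9% | 40.2 / 44.3% | 41.5 / 45.6% |
| Odds ratio 1.6 | 38.4% | 28.4 / 31.3% | 29.1 / 32.1% |
| Mortality of 60% | 60% | 98.7 / 99.4% | 99.0 / 99.5% |
| Increase of 60 points | 88% | 100% | 100% |
| 60% relative decrease | 11.2% | 76.8 / 81.6% | 81.3 / 85.6% |

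**Choice of test.** For the relative increase, unpooled, arcsine, exact chi-square and Freedman log-rank versions all fall between 59% and 67%. Fisher's exact test gives 54.0 / 60.2%. One-sided testing reaches at most 77.5%.

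**What 80% would need for 28% to 44.8%.** Events: 4 × (1.960 + 0.842)² / (ln 1.81)² ≈ 89.4, so about 90 deaths against 58–66 expected. Per group: 89.4/0.728 ≈ 123 by log-rank, or 128 by two proportions.

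**Detectable at 80% power from 28%** (n = 80 / n = 90):
- Relative increase: 74.6 / 70.3% by log-rank; 76.5 / 72.0% by two proportions.
- Relative decrease: 59.3 / 56.7% by log-rank; 62.0 / 59.0% by two proportions.

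**Sensitivity to the base rate, 60% relative increase** (n = 80 / n = 90):
- Base 23%: 47.8 / 52.5% by two proportions, 49.5 / 54.2% by log-rank.
- Base 34%: 74.3 / 79.2% by two proportions, 76.3 / 81.0% by log-rank.
- 80% power needs a base of about 34–37%.

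**28% as a yearly rate.** With HR 1.6 and an assumed 5 years of follow-up, log-rank power is 77.0 / 81.6%. The result depends on the assumed duration: 67–72% at 3 years, 79–84% at 6. At 5 years it implies conservative-group mortality of 1 − e^(−0.28 × 5) = 75%.

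**The case against.** The strongest reply is that one word is wrong and the 80% is essentially right. With a decrease in place of an increase, the two-proportion detectable effect is 62% at 80 per group and 59% at 90. That fits both the stated effect of about 60% and the claim of robustness between the two sample sizes. It also fits the transplant survival in section 3.3.2. On that reading the 60–67% does not describe the study's power for its intended effect. This explanation is plausible and may be the likeliest, but it remains an inference. If it is right, the plan names the wrong direction for a primary comparison and still needs correcting.

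The yearly-rate reading also comes near 80%, but its implied 75% five-year mortality is far from the protocol's 23%–34%.

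The log-rank figures only approximate the planned analysis. They ignore propensity adjustment and assume equal follow-up and proportional hazards. That stands as a caution against false precision, but the two-proportion results agree with them to within about 2 points for the relative increase.

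Finally, the 185 patients are a projected available population, and neither enrolment nor stopping depends on this calculation. That limits the consequence to what is claimed and how a null result is read. For a primary outcome, that still matters.

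**Conclusion.** The sentence is wrong as written. With 28% as cumulative mortality, 80 to 90 per group and two-sided alpha 0.05, no reading of an increase yields 80%. The natural one, a relative increase to 44.8%, has about 60–67% power, so such a rise would be missed about 33–40% of the time. A 60% relative decrease comes close to the stated figure, at 77–86% depending on test and group size.

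Confidence is high that the figure does not reproduce. No single corrected power can be asserted until the sponsor states direction, scale, horizon and test. In either direction, the smallest effect detectable at 80% power is a relative change of more than half, which is hard to call moderate.

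**What to change.** In section 6.2, state the direction, whether 60% is relative or absolute, the period to which 28% applies, and the test. Then give the matching power, preferably for the planned log-rank/Cox analysis:

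- If a decrease was meant: *about 81% (80 per group) to 86% (90 per group) power by log-rank (Schoenfeld), or 77–82% by two proportions, for a 60% relative decrease in mortality from 28% to 11%.*
- If an increase was meant: *about 62% (80 per group) to 67% (90 per group) power by log-rank (Schoenfeld), or 60–65% by two proportions, for a 60% relative increase in mortality from 28% to 45%.*

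Replace the statement of adequate power for a moderate mortality difference with what is detectable at 80% power by log-rank: a relative increase of about 70–75%, or a relative decrease of about 57–59%.

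As a useful addition, commit to reporting the mortality comparison with a 95% confidence interval. Even with 28% mortality in both groups, the half-width for the risk difference is 1.96 × √(2 × 0.28 × 0.72/n): 13.9 points at n = 80 and 13.1 at n = 90.

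The cost is one or two restated sentences, with no extra patients and no change to the analysis. The only downside is a less favourable stated power if an increase was meant.

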## 7. Data Management

**Aim 1:** All study data will be collected via systems created in collaboration with the RDCRN Data Management and Coordinating Center and will comply with all applicable guidelines regarding patient confidentiality and data integrity.

**Aim 2 and 3:** All qualitative study data (i.e. interview and focus group transcriptions) will be collected by research partners at the GW Milken Institute School of Public Health and managed by GW investigators using QSR International NVivo 10 software [[http://www.qsrinternational.com/products\\_nvivo.asp](http://www.qsrinternational.com/products_nvivo.asp)]. After qualitative study data collection efforts are complete, data will be exported from NVivo to text files and submitted to the RDCRN Data Management and Coordinating Center.

### 7.1. Registration

Registration of participants on this protocol will employ an interactive data system in which the clinical sites will attest to the participant's eligibility as per protocol criteria and obtain appropriate informed consent. IRB approval for the protocol must be on file at the DMCC before accrual can occur from the clinical sites.

The DMCC will use a system of coded identifiers to protect participant confidentiality and safety. Each participant enrolled will be assigned a local identifier by the enrollment site. This number can be a combination of the site identifier (location code) and a serial accession number. Only the registering site will have access to the linkage between this number and the personal identifier of the subject. When the participant is registered to participate in the study, using the DMCC-provided web-based registration, the system will assign a participant ID number. Thus, each participant will have two codes: the local one that can be used by the registering site to obtain personal identifiers and a second code assigned by the DMCC. For all data transfers to the DMCC, both numbers will be required to uniquely identify the subject. In this fashion, it is possible to protect against data keying errors, digit transposition or other mistakes when identifying a participant for data entry since the numbers should match to properly identify the participant. In this fashion, no personal identifiers would be accessible to the DMCC.

### 7.2. Data Entry

**Aim 1:** Data collection for this study will be accomplished with online electronic case report forms. Using encrypted communication links, on-line forms will be developed that contain the requisite data fields.

**Aim 2 and 3:** Interviews and focus groups will be audio recorded with participant permission and transcribed. All audio recordings will be deleted following their transcription and transcriptions will be uploaded to a QSR International NVivo 10 software database, which will be password protected and stored on a secure hard drive with access limited to designated investigators.

## 8. Human Subjects

### 8.1. GCP Statement

This study will be conducted in accordance with the ethical principles that have their origin in the Declaration of Helsinki, and that are consistent with Good Clinical Practice and all applicable regulatory requirements.

### 8.2. Risks (and Protection Against Risks)

The primary risk is a breach of confidentiality and privacy. However, the study staff is trained in procedures for maintaining the security and confidentiality of data. All files will be stored in a locked suite on a secure floor in the Children's Research Institute, or The George Washington University, or in a locked suite at the National Urea Cycle Disorders Foundation. However, the primary research coordinator at the Children's Research Institute will house copies of all relevant study materials. Study databases will be password-protected, and all staff will be trained in the importance of maintaining the confidentiality of study data.

While participation in interviews or focus groups does not pose any physical risks to subjects, caretakers, or providers, some questions may make subjects feel uncomfortable or anxious. Participants will be informed of their right to stop the interview at any time and/or decline to answer any question. We will facilitate online interviews and focus group discussions for patients and families who do not ordinarily attend NUCDF meetings and consider extra time and travel to be burdensome.

Because of neuropsychological testing, the participants could find out that they have an intellectual disability. However, developmental testing is also part of routine care; the participant might find out they have an intellectual disability regardless of involvement in the study.

